10.4. Appendix 4: Summary of Protocol Amendments

Protocol Amendment 1, Protocol version 2.0, dated 24 June 2020

The study protocol has been amended to address comments raised by the FDA and IRB following their review of the original protocol, Protocol version 1.0, dated 06 May 2020. Major changes are summarised below.

Administrative and minor grammatical, editorial, and formatting changes were made for clarification purposes only.

Section 1.1

- Secondary endpoints were revised to include data at Day 21 and Day 42, and not Day 28.
- Exploratory objective and endpoints revised to include detection of EDP1815 in stool and/or in blood.
- Participant Trial Duration revised to 42 days post first dose.

Section 1.2

- Schema revised to indicate longer study duration to 42 days post first dose.

Section 1.3

- Schedule of Assessments revised to indicate longer study duration to 42 days post first dose, including assessments to be performed.
- The following assessments were added to the Schedule of Assessments:
 - Smoking status.
 - Significant Covid-19 Comorbidities.
 - Plasma PCR for EDP1815.
- The timing of the following assessment was changed:
 - Faecal sample for microbiome analysis
- Schedule of Assessments footnotes revised:
 - to add surveillance for potential GI symptoms.
 - to clarify assessments to be collected in the event of remaining in hospital longer than 14 days.
 - to clarify faecal sample collection.
 - to add information on smoking status.

Section 3

- Secondary endpoints were revised to include data at Day 21 and Day 42, and not day 28.

- Exploratory objective and endpoints revised to include detection of EDP1815 in stool and/or in blood.
- Participant Trial Duration revised to 42 days post first dose.

Section 4.4

- End of Study Definition revised to indicate longer study duration to 42 days post first dose.

Section 5.1

- Inclusion criteria revised/clarified:
 - to include participants receiving any form of supplementary oxygen therapy at baseline.
 - to include participants with confirmed COVID-19 viral infection by RTPCR at screening.
 - Age:
 - 18-75 years old., OR
 - 15 - 17 year-olds can be included after DMC approval (see section 10.1.5), OR
 - >75 year-olds can be included after DMC approval (see section 10.1.5).
- Removed the following inclusion criterion:
 - Are considered an appropriate subject for intervention with EDP1815 in the opinion of the investigator.

Section 5.2

- Exclusion criteria revised/clarified;
 - to exclude participants with a diagnosed primary immunodeficiency.
 - to allow the use of laboratory results reported in the last 48 hours.
 - to exclude participants with GI signs or symptoms equivalent to CTCAE v5.0, gastrointestinal disorders, grade 3 or 4 event.
 - clarified the exclusion if participants are currently participating in an interventional study.

Section 6.1

- Clarified the minimum time allowed between the twice daily doses.

Section 6.6.1

- Amended the study stopping criteria:
 - One (or more) subjects on treatment with EDP1815 has symptoms of a clinically significant bacteremia and has a positive blood culture for the EDP1815 strain of

P. histicola.(Note: the study will be paused and dosing held in all participants while identifying the specific strain of P.histicola).

Section 7.2

- Revised to include sub section 7.2.1, Temporary Cessation of Dosing in an Individual Participant and section 7.2.2, Permanent Cessation of Dosing in an Individual Participant.

Section 8.1.3

- Clarified that the dairy should be completed until the participant is asymptomatic and off oxygen for at least 48 hours or to Day 42, whichever is sooner.

Section 8.1.4

- Revised in line with longer duration of study.

Section 8.2

- Revised to include sub section 8.2.3: Strain-specific PCR for EDP1815 and section 8.2.4: Gastrointestinal Assessment.

Section 8.3

- Revised to include reference to the CTCAE grading of adverse events, including addition of wording related to collection of adverse events relating to GI adverse events.

Section 8.6

- Addition of section on Additional Baseline Information.

Section 9.4.1.1

- Addition of wording on handling newly approved medication for COVID-19 becoming a potential covariate.

Section 9.4.1.2

- Revised days in relation to the longer study duration.
- Addition of wording on handling newly approved medication for COVID-19 becoming a potential covariate.

Section 9.4.1.3

- Addition of wording on handling newly approved medication for COVID-19 becoming a potential covariate.

Section 9.5

- Revised wording to indicate the DMC involvement prior to enrolling participants aged 15-17, as well as participants aged >75 years.

Section 10.1.5

- Revised wording to clarify DMC membership and to indicate the DMC involvement prior to enrolling participants aged 15-17, as well as participants aged >75 years.

Section 10.3

- Revised classification of adverse events to use the CTCAE classification.
- Revised the SAE reporting wording with inclusion of contact telephone numbers and email address.

Protocol Amendment 2, Protocol version 3.0, dated 09 July 2020

The study protocol has been amended to address comments raised by the FDA following their review of Protocol version 2.0, dated 24 June 2020. Major changes are summarised below.

Administrative and minor grammatical, editorial, and formatting changes were made for clarification purposes only.

Section 1.3

- An HIV assessment at the time of screening was added to the Schedule of activities
- An ‘x’ was added to the screening visit for concomitant medications and adverse event checks.

Section 5.1

- The inclusion criteria were amended to an age range of 18-65 years old. Inclusion of subjects aged 15-17 years was removed; and text related to possible inclusion of subjects older than 65 after DMC review was added.

Section 5.2

- The exclusion criteria were amended to add individuals with HIV/AIDS.

Section 7.2.2

- Permanent cessation of dosing in an individual participant criteria were updated to include a diagnosis of HIV/AIDS.

Section 8.4

- Additional antibiotic options added in case of penicillin allergy.

Sections 9.5 and 10.1.5

- An update was made to the DMC review criteria, to include assessment after 20 subjects are enrolled for consideration of enrolling patients older than 65, and removal of consideration of enrolling adolescents aged 15-17.

Protocol Amendment 3, Protocol version 4.0, dated 03 August 2020

The study protocol has been amended to include biobanking language and to clarify the collection of the microbiome sample and what the site should do in the event of a positive blood culture during the study. Major changes are summarised below.

Administrative and minor grammatical, editorial, and formatting changes were made for clarification purposes only.

Page 13, Section Number of Centers

- Language changed to accommodate increase in number of potential sites to be utilized in the study to meet enrolment goals.

Section 1.3

- Biomarker sample added to the Schedule of Activities (SOA)
- SOA Footnote #7: language added to clarify when the Microbiome Sample should be collected.

Section 8.2.3

- Language added to clarify what should be done at the site level should there be a participant showing signs of bacteremia with a positive blood culture.

Section 8.5.4

- Language added to clarify when the Microbiome Sample should be collected.

Section 8.5.5

2 Abbreviations and Definitions

AE	Adverse event
ANCOVA	Analysis of covariance
BMI	Body mass index
CI	Confidence interval
CRC	Covid related complications
CRF	Case report form
CRP	C-reactive protein
CSR	Clinical study report
CTCAE	Common terminology criteria for adverse events
dp	Decimal place
eCRF	Electronic case report form
FiO2	Fraction of inspired oxygen
GI	Gastrointestinal
iDMC	Independent data monitoring committee
ICU	Intensive care unit
IMP	Investigational medical product
ITT	Intention to treat
LDH	Lactate dehydrogenase
LS	Least squares
MedDRA	Medical Dictionary for Regulatory Activities
MMRM	Mixed model for repeated measures
MNAR	Missing not at random
O2	Oxygen
OSCI	Ordinal scale for clinical improvement
PCI	Potentially clinically important
RTPCR	Reverse transcription polymerase chain reaction
SAE	Serious adverse event
S/F Ratio	SpO2/FiO2 ratio
SOC	System organ class
SpO2	Oxygen saturation by pulse oximetry
SAP	Statistical analysis plan
SD	Standard deviation
SE	Standard error
ULN	Upper limit of normal
WHO	World Health Organization

3 Introduction

The purpose of this SAP is to provide all information that is necessary to perform the required statistical analyses of study EDP1815-205. It also defines the summary TFLs to be included in the final clinical study report according to the protocol. The SAP is based upon, and assumes familiarity, with the study protocol, version 4.0, dated 05-Aug-2020.

If a future protocol amendment necessitates a substantial change to the statistical analysis of the study data, this SAP will be amended accordingly. The content of this SAP is compatible with the ICH E9 Guidance document.

4 Study Objectives and Endpoints

4.1 Study Objectives

The primary objective of the study is

- To evaluate the effect of EDP1815 on pulmonary function as measured by the change in Oxygen Saturation by Pulse Oximetry (SpO₂) / Fraction of Inspired Oxygen (FiO₂) [S/F ratio]

Secondary objectives of the study are:

- To evaluate the effect of EDP1815 on the development and severity of complications of COVID-19 infection
- To evaluate the effect of EDP1815 on length of hospitalization and recovery in participants with COVID-19
- To evaluate the safety and tolerability of EDP1815 in participants with COVID-19

Exploratory objectives of the study are:

- To evaluate the effect of EDP1815 on the exaggerated host cytokine response to COVID-19 infection
- To identify clinical or biochemical predictors of response to EDP1815

4.2 Endpoints

Table 1 List of endpoints associated with each study objective

Objectives	Endpoints
Primary	

• To evaluate the effect of EDP1815 on pulmonary function as measured by the change in S/F Ratio	
• Change from baseline to the lowest S/F ratio measured in days 1-14

Objectives	Endpoints
Secondary	

 To evaluate the effect of EDP1815 on the development and severity of complications of COVID-19 infection 	
 Change in S/F ratio at days 4, 7, 10 and 14/discharge day. Percentage change in S/F ratio at days 4, 7, 10 and 14/discharge day. Percentage of participants at each level on the WHO OSCI score at days 4, 7, 14, 21 and 42. Percentage of participants with shifts from each level of the WHO OSCI score at baseline at days 4, 7, 14, 21 and 42. Percentage of participants remaining at their baseline score on the WHO OSCI (or lower) at days 4, 7, 14, 21 and 42. Percentage of participants reporting each level of the WHO OSCI score at their worst post-baseline day. The time in days spent at each participant's worst reported WHO OSCI score (excluding death). Intubation and mechanical-ventilation free survival, defined as the time in days from start of treatment to first occurrence of a WHO OSCI score of 6 or more. Overall survival, defined as the time in days from start of treatment to death by any cause Number of days requiring oxygen therapy. Number of days with pyrexia $\geq 38^{\circ}\text{C}$. Maximum daily temperature. Minimum SpO₂ level. Maximum SpO₂ level.

 To evaluate the effect of EDP1815 on length of hospitalization and recovery in participants with COVID-19 	
 Time to discharge, defined as the time in days from start of treatment to first occurrence of a WHO OSCI score of 2 or less. Time to oxygen saturation (SpO₂) $\geq 94\%$ on room air without further requirement for oxygen therapy. Time to recovery, defined as the time in days from symptom onset to alleviation of all COVID-19 symptoms.

Objectives	Endpoints
Exploratory	

To evaluate the effect of EDP1815 on the exaggerated host cytokine response to COVID-19 infection	
Change from baseline in cytokine levels (including IL-6) at day 4 and day 7 (and/or at additional timepoints if samples are available).Change from baseline in inflammatory response at day 4 and day 7 (and/or at additional timepoints if samples are available).

To identify clinical or biochemical predictors of response to EDP1815.	
Statistical significance of each potential predictor-treatment interaction in exploratory models based on the final selected model for the primary efficacy analysis.To identify the presence of EDP1815 in stool and/or blood using PCR primers

5 Study Methods

5.1 General Study Design and Plan

This is a double-blind, placebo-controlled parallel group study to assess the efficacy and safety of EDP1815 in the treatment of patients hospitalized by SARS-CoV-2 infection.

[figure not shown]
This is a pilot study designed to investigate the potential of EDP1815 in the prevention of COVID-19 disease progression.

60 participants who are hospitalized with confirmed COVID-19 disease will be randomized in a 1:1 ratio to EDP1815 and matching placebo, in addition to standard of care. The study may be extended to an additional 40 subjects, based on recommendations from an independent data monitoring committee (iDMC).

The study will comprise of a Screening Phase, a 14-day Treatment Phase and a 28-day Follow-up Phase as shown in [Figure 1](#).

- Due to the urgent nature of the study, the screening phase may occur on the same day as the start of the treatment phase with eligible participants dosed as soon as possible after eligibility is confirmed.
- The treatment course is 14 days with twice daily dosing for the first 3 days followed by once daily dosing for the remainder of the treatment period.
- Participants who are discharged prior to the end of the follow-up period will remain in the study and complete a daily questionnaire on until their symptoms have resolved or the end of the follow-up period (whichever occurs first)
- Participants who are discharged prior to the end of the 14-day treatment period, will have medication dispensed to take at home.

Figure 1 Study Schema

5.2 Randomization and Blinding

Participants will be randomly allocated, in a 1:1 ratio, to EDP1815 or matched placebo using a pre-prepared, blocked randomization list. Randomization numbers will be allocated sequentially. If more than one site is used in this study each site will be given complete blocks of randomization numbers.

The study will be fully blinded to the participants, site staff and sponsor. An independent statistics and programming group will be used to prepare all unblinded outputs for the iDMC which will be held in a secure area until the study has completed.

The Sponsor must be notified immediately (within 24 hours) if the investigational drug blind is broken. The date, time, and reason the blind was broken must be recorded on the appropriate Case Report Form (CRF).

5.3 Derived variables

5.3.1 General

5.3.1.1 Relative Day and Time

The relative day of an assessment will be calculated as:

- For measurement performed on or after the date of first dose:
Date of assessment – date of start of treatment +1
- For measurements performed before the date of first dose:
Date of assessment – date of study treatment

5.3.1.2 Baseline

The last non-missing value collected before first study dose will be taken as the baseline measurement for all parameters. If data is collected on Day 1 without an associated time being provided, it will be assumed to be pre-dose.

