1.3. Schedule of Activities (SoA)

Figure 2: Schedule of Activities

Data	Screening [^] (Day -1 to Day 0)	Baseline [^] (Day -1 to Day 0)	D 1 [^]	D 2	D 3	D 4	D 5	D 6	D 7	D 8	D 9	D 10	D 11	D 12	D 13	D14 or day of discharge ^{&}	D21 ~ (Follow-up Telephone Visit)	D42 (Final Follow-Up Telephone Visit)
Informed consent	x																	
Inclusion and exclusion criteria	x																	
Demographics and anthropomorphic data (e.g. age, height, weight)	x																	
Smoking status ⁹	x																	
Medical history	x																	
Significant Covid-19 Comorbidities	x																	
Physical examination	x																	
Pregnancy test (blood/urine) ¹	x																	
Vital signs ^{#*}		x	x	x	x	x	x	x	x	x	x	x	x	x	x	x		
Concomitant Medications [#]	x	x	x	x	x	x	x	x	x	x	x	x	x	x	x	x	x	
Oxygen therapy status [#]		x	x	x	x	x	x	x	x	x	x	x	x	x	x	x	x	
SaO ₂ /FiO ₂ status ^{#2*}		x	x	x	x	x	x	x	x	x	x	x	x	x	x			
Blood tests (FBC, CRP, LFT, Creatinine, Urea and Electrolytes, Ferritin, D-		x				x ³			x ³									

Data	Screening [^] (Day -1 to Day 0)	Baseline [^] (Day -1 to Day 0)	D 1 [^]	D 2	D 3	D 4	D 5	D 6	D 7	D 8	D 9	D 10	D 11	D 12	D 13	D14 or day of discharge ^{&}	D21 ~ (Follow-up Telephone Visit)	D42 (Final Follow-Up Telephone Visit)
dimer, Troponin) ^{#*}																		
HIV test	x																	
Cytokine Panel, Paxgene sample, and Biobanking sample*		x				x ³			x ³									
Plasma PCR for EDP1815									x ³									
Day since onset of symptoms [#]		x																
8-point ordinal scale [#]		x	x	x	x	x	x	x	x	x	x	x	x	x	x	x	x	x
COVID-19 RTPCR [#]	x																	
Review of adverse events ^{#*@}	x	x	x	x	x	x	x	x	x	x	x	x	x	x	x	x	x	x
Retrieval of relevant clinical data ⁴																		x
Outpatient questionnaire ⁵			x	x	x	x	x	x	x	x	x	x	x	x	x ⁶	x ⁶	x ⁶	
Telephone call ⁵								x							x	x	x	
Discharge status [#]			x	x	x	x	x	x	x	x	x	x	x	x	x	x	x	
Mortality status [#]			x	x	x	x	x	x	x	x	x	x	x	x	x	x	x	
Faecal sample for microbiome analysis		x ⁷							x ⁷									
EDP1815 or Placebo administration ⁸			x ⁸	x ⁸	x ⁸	x	x	x	x	x	x	x	x	x	x			

[^] Due to the urgent nature of the study, screening, baseline and Day 1 assessments can occur on the same day. Eligible patients will be randomized and dosed as soon as possible after eligibility is confirmed.

[~] This assessment can be performed between days 20-22.

#Results will be extracted from the patient record where available – no research specific test may be required.

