5.3.3.4 WHO OSCI

The WHO OSCI has values ranging from 0 to 8 as shown in [Table 6](#).

Table 6 WHO Ordinal Scale for clinical Improvement

Participant State	Descriptor	Score
Uninfected	No clinical or virological evidence of infection	0
Ambulatory	No limitation of activities	1
	Limitation of activities	2

Participant State	Descriptor	Score
Hospitalized – Mild disease	Hospitalized, no oxygen therapy	3
	Oxygen by mask or nasal prongs	4
Hospitalized – Severe Disease	Non-invasive ventilation or high flow oxygen	5
	Intubation and mechanical ventilation	6
	Ventilation + additional organ support	7
Dead	Death	8

The WHO OSCI will be recorded daily in the eCRF while participants remain in hospital. Once discharged, the WHO OSCI will be derived from questions 1 and 2 of the daily COVID-19 diary using the rules defined in [Table 7](#).

Table 7 Derivation of WHO OSCI using the Outpatient Daily Covid-19 diary

Question 1: Overall, how severe were your COVID-19 symptoms today?	Question 2: How much did your COVID-19 symptoms interfere with your usual activities today?	WHO OSCI Score
No COVID-19 symptoms today	Any response	0
Mild, moderate, severe or very severe	Not at all	1
Mild, moderate, severe or very severe	Somewhat or Very much	2

For participants who report question 1 as “No COVID-19 symptoms today” and a return to their usual activities (Q3) for 2 days in a row do not need to complete the COVID-19 diary on subsequent days. If this condition is met, the missing WHO OSCI score will be imputed as 0 for any remaining study days up to and including Day 42.

Note that participants who are discharged on home oxygen will still be considered as having WHO OSCI score =2 as the participant state is considered before the descriptor in [Table 6](#).

For participants who die, the WHO OSCI score will be imputed to 8 for all remaining study days after death.

WHO OSCI scores that are missing for reasons other than death or full recovery of symptoms will not be imputed.

For the secondary endpoint looking at whether participants remained at or below their baseline WHO OSCI score at Days 4, 7, 10, 14, 21 and 42, participants who show an increased score and then return to their baseline score (or lower) will not be considered as having met the criterion for this endpoint. Only participants who have not reported a score above their baseline score on any day prior to the endpoint day will be considered as having met the endpoint for that day.

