5.3.3.8 Temperature and Number of Days with Pyrexia $\geq 38^{\circ}\text{C}$

Temperature will be reported daily for participants prior to discharge. The daily temperature reported on the CRF should be the highest recorded in the participant notes for that day.

After discharge, participants are asked to report their temperature daily while they are still experiencing symptoms if they have a thermometer at home. If they do not have a thermometer at home, they should answer a question on the daily diary to say if they feel like they have a fever.

In the event that a subject reports data in both the patient diary and on the vital signs CRF for a single study day, both measurements will be listed but the temperature collected on the CRF vital signs page will be used in the tables and figures.

Temperature may be recorded in $^{\circ}\text{C}$ or $^{\circ}\text{F}$. Temperature recorded in $^{\circ}\text{F}$ will be converted to temperature in $^{\circ}\text{C}$ as follows:

$$\text{Temperature } (^{\circ}\text{C}) = (\text{Temperature } (^{\circ}\text{F}) - 32) * (5/9)$$

Temperature ($^{\circ}\text{C}$) will be presented to 1 dp in the listings.

Each study day will be flagged as with or without pyrexia $\geq 38^{\circ}\text{C}$ based on the actual data reported.

Number of days with pyrexia $\geq 38^{\circ}\text{C}$ will be reported for the following intervals:

- Days 1-14
- Days 1-28
- Days 1-42

For each interval, the percentage of days with pyrexia $\geq 38^{\circ}\text{C}$ reported will be calculated, using the number of days with a temperature measurement recorded as the denominator.

As temperature data is expected to be missing not at random (MNAR), i.e. that the reason for missingness may be dependent on the missing value (were it to have been observed), an alternative method for counting days with pyrexia will be used for sensitivity analyses as detailed below:

- Missing temperature measurements because a participant has died or withdrawn from the study
 - Days after death/withdrawal will be counted as having pyrexia $\geq 38^{\circ}\text{C}$
- Missing temperature measurements while participant is still in hospital
 - If there exists at least one temperature measurement within 1 day of the missing measurement, it will be imputed with the average of the measurements reported within the window of $+\text{-} 1$ day

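### If WHO OSCI carries no clock time, SAP 5.3.1.2 lets a Day 1 score that arose after dosing replace the Baseline-visit score

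*SAP*

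**What the plan says.** SAP 5.3.1.2 sets one baseline rule: "The last non-missing value collected before first study dose will be taken as the baseline measurement for all parameters". It then deals with missing times: "If data is collected on Day 1 without an associated time being provided, it will be assumed to be pre-dose". No parameter is exempted, and no preference is given to the record from the Baseline visit.

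SAP 5.3.1.1 numbers days from first dose as "Date of assessment – date of start of treatment +1", so Day 1 is the calendar date of first dose and a Day 1 record may fall on either side of it. In the Schedule of Activities (Protocol 1.3), the row "8-point ordinal scale" is ticked under Baseline (Day -1 to Day 0) and again under D1, as are vital signs. The same table allows that "screening, baseline and Day 1 assessments can occur on the same day".

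On how the two measures are recorded, SAP 5.3.3.4 says "The WHO OSCI will be recorded daily in the eCRF while participants remain in hospital" and mentions no time of day. SAP 5.3.3.8 says of temperature: "The daily temperature reported on the CRF should be the highest recorded in the participant notes for that day".

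Baseline OSCI is used in the shift tables (SAP 9.3.3.2), as a candidate covariate with levels 4 and 5 (SAP 7.2), as a tabulated risk factor when the score is 5 (SAP 8.4), and in the endpoint of staying at or below the baseline score. SAP 5.3.3.4 makes that last endpoint strict. It is met by "Only participants who have not reported a score above their baseline score on any day prior to the endpoint day", so a later return to baseline does not restore a participant.

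**The concern.** A baseline should be known to precede treatment. Here a record that is known to be pre-dose can be replaced by one whose timing is unknown, for the sole reason that its time was not captured. When the Day 1 score reflects deterioration after the first dose, that deterioration moves into baseline and is no longer counted as an outcome.

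The strict endpoint is the most exposed. One Day 1 step-up, judged against the Baseline-visit score, is a failure at every reported day (4, 7, 10, 14, 21 and 42). Judged against the Day 1 score, it is a success unless the participant worsens further.

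The SAP also takes the opposite view elsewhere. An adverse event on the treatment start date with no time is given the time of first dose (SAP 7.3.2) and so counts as treatment-emergent (SAP 5.3.4.2). One deterioration on Day 1 could therefore be a treatment-emergent event in the safety tables and part of baseline in the efficacy tables.

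**Working it through.** The plan states no figure on this point, so there is none to reproduce. The check applies the rule to a constructed participant and then sizes the effect.

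**Step 1. Which record becomes baseline.** Suppose the Baseline visit is the day before dosing and the Day 1 score is untimed. SAP 5.3.1.2 classes both records as pre-dose, and the Day 1 record is the later of the two, so it is baseline. If the Day 1 record had a documented post-dose time, the Baseline-visit record would stand. If both visits fall on one date and neither record is timed, both count as pre-dose and the rule does not say which is last.

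**Step 2. A worked path.** OSCI is 4 at the Baseline visit, 5 on Day 1 (after dosing, untimed), 5 on Days 2 to 4, 4 on Days 5 and 6, and 3 on Day 7.

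| | Baseline = Day 1 score (5) | Baseline = Baseline-visit score (4) |
|---|---|---|
| Never above baseline, Day 4 | met | failed |
| Never above baseline, Day 7 | met | failed |
| Shift at Day 4 | 5 - 5 = 0 | 5 - 4 = +1 |
| Shift at Day 7 | 3 - 5 = -2 | 3 - 4 = -1 |

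**Step 3. Weight of one participant.** Sixty participants randomized 1:1 (Protocol 9.1) give 30 per arm, and 1/30 = 3.3 percentage points. If the study is extended to 100 with 50 per arm, 1/50 = 2.0 points.

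**Step 4. Range over assumed frequencies.** Let w be the share of an arm that steps up on Day 1 after dosing, with no time recorded and a separate earlier Baseline record. Let q be the share of those who later worsen further and fail anyway. The overstatement of the proportion is w(1 - q). Both inputs are assumptions.

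| w | q = 0 | q = 0.5 |
|---|---|---|
| 5% | 5.0 points | 2.5 points |
| 10% | 10.0 points | 5.0 points |
| 20% | 20.0 points | 10.0 points |

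**Step 5. Effect on a difference.** Assume true proportions of 85% and 70%, and that the same fraction f of the worsening in each arm is absorbed into baseline. The difference becomes [1 - 0.15(1 - f)] - [1 - 0.30(1 - f)] = 0.15(1 - f). For f = 10%, 20% and 30%, the 15-point difference shrinks to 13.5, 12.0 and 10.5 points. This illustrates the direction and is not a forecast.

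**Step 6. Temperature.** The Day 1 CRF value is the day's maximum, so it may come from after dosing. Baseline temperature appears only in the summary of baseline disease characteristics (SAP 8.3). Pyrexia days and maximum temperature use no baseline (SAP 5.3.3.8 and 9.3.6). The change-from-baseline summary of vital signs covers blood pressure, pulse and respiration only (SAP 10.5.1).

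**The case against.** The strongest reply is that the problem is conditional and the rule has a purpose.

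- **It depends on the eCRF.** The rule bites only on untimed records. The documents do not say whether OSCI is timed, and SAP Section 8 promises assessment times in listings only where applicable. This stands, and it is why the point is worded conditionally.
- **OSCI is not defined as a whole-day or worst-of-day score.** It is only said to be recorded daily, so the Day 1 entry may be a single assessment made before dosing. This stands: the defect is that the timing is unknown, not that the score is known to be post-dose.
- **The rule protects same-day baselines.** When Baseline and Day 1 share a date, the Baseline-visit record is itself Day 1 data and would be lost if untimed values were treated as post-dose. SAP 5.3.2.7 also provides for participants who enter too late on Day 1 for two doses, and for them most of that day is pre-dose. This is a fair reason for having some such rule, but the visit label can protect those records without letting a D1 record displace them.
- **Reversing the rule brings the opposite error.** A participant who truly worsened on Day 1 before dosing, with no time recorded, would fail the strict endpoint at every later day. This also stands. But pre-dose worsening cannot depend on treatment, so randomization should balance it between arms. Post-dose worsening may depend on treatment.
- **The stakes are limited.** The affected outputs are secondary, and SAP Section 9 calls all analyses descriptive. Baseline OSCI enters a model only if stepwise selection retains it among at most three added covariates (SAP 7.2 and 9.1.1.2). A Day 1 score outside levels 4 and 5 should be noticed at the blinded review. This argues for modest priority, not for leaving the sentence as it is.

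**Conclusion.** The point holds in conditional form. If OSCI has no recorded time, the plan as written makes the Day 1 score baseline in place of a Baseline-visit score known to be pre-dose. A first-day step-up after dosing then disappears from the shift table and can turn failure into success on the strict endpoint. Each such participant is worth 3.3 points in an arm of 30. The rule is blind to treatment, so the expected consequence is hidden early worsening and dilution of any difference.

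A reader might infer more than the documents support:

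- **That displacement will certainly happen.** This needs knowledge of the eCRF, which the documents do not give.
- **That the endpoint is overstated by a particular amount.** Nothing in the documents says how many participants worsen on Day 1 after dosing. The figures in Steps 4 and 5 are only as good as their assumed inputs.
- **That one arm is favoured.** The rule applies identically to both.
- **That the temperature results are distorted.** Only one descriptive baseline table is affected.
- **That the primary result is shown to be wrong.** The rule does cover S/F ratio as one of all parameters. But the documents do not say whether S/F records are timed, or whether a value used as baseline also stays in the Days 1-14 trough, so no such effect is concluded here.

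**What to change.** Amend SAP 5.3.1.2 to read:

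> Baseline is the last value documented as before first dose, or the record labelled as the SoA Baseline visit (including when Baseline and Day 1 fall on the same date). An untimed D1-visit record is used as baseline only if no Baseline-visit record exists; otherwise it is post-baseline.

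This covers OSCI and temperature together and keeps untimed same-day baselines through the visit label. If the eCRF does capture a time for OSCI, a statement to that effect in the SAP would remove most of the concern, and the amended sentence would then matter only for records where the time is missing.

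The cost is a short SAP edit and a visit-label check in programming, with no new data. The downside should be stated alongside it: a true pre-dose worsening on Day 1 with no recorded time will count as post-baseline. Randomization should balance that between the arms.
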